size based on the observed differences in outcomes such as HRQoL (SF-36 and prostate cancer index, PCI) and cost of PCa care across groups. The primary outcome is HRQoL as measured by the SF-36 and PCI sub-scales. A change of 5 to 9 points on PCI is clinically meaningful [272]. Similarly, a difference of 7 points or more on the SF subscales is considered clinically meaningful [272, 275, 301]. Based on our prior research and that of Litwin et al [253, 272], the standard deviations for the PCI and SF-36 scales in samples of men with PCa mostly range from 8 to 14; hence standardized differences (SDs) of $7/14=0.5$ to $7/8=0.87$ will be clinically relevant. The power calculations for Aims 2-4 assume availability of 720 participants who are eligible for randomization into one of the two intervention groups. We assume a conservative intra-class correlation of 0.3 and 4 follow-up measures per subject. The sample size is adjusted to accommodate a 10% missing or dropout rate by 24 months based on rates over a similar period of time in previous studies [272, 275, 301]. We assume 80% power and two-sided level of significance of $\alpha = 0.05$. We have 80% power to detect a 1.2 point difference in PCI or SF-36 sub-scale. Within treatment type, the sample size is reduced to 60 per intervention arm. We have 80% power to detect a 3.0 point difference in sub-scale with 60 patients in each arm. Thus, we will have adequate power to detect differences between treatment groups [302]. Power for identifying utility based profiles and outcomes: We analyzed the levels of power for differences in outcomes between profiles defined by latent classes of attributes-specific utilities with a conservative allocation of subjects to each profile (25 in one vs. 10 in other profile) and less conservative allocation (35 in one profile vs. 35 in other profile) using a logistic model based comparison for a binary outcome (e.g. recovery of baseline HRQoL) with a 2-sided alpha of .0125 (Holms adjustment profiles). In the first allocation, the group difference of 0.56 yields 80% power; for the second allocation an effect size of 0.42 corresponds to power of 90. Thus, with our anticipated effect size of 0.51, we will have adequate power with $n=60$ in each group. (Adjusting for patient characteristics may reduce the effect sizes of the differences between profiles.)

Key inclusion criteria

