patients in decision (measured using CPS) using multi-nominal regression model to adjust for observed covariates. Then we will examine if these associations vary across intervention and usual care control groups. We then will repeat the model with other independent variables (decision conflict and trust). Next, we will test the association denoted by path c (direct effect of DCS, CPS, and trust on outcomes). For continuous outcomes (HRQoL, AUA-SI, MAX-PC, CES-D, SWD, and PSQ-18), we will compute area under the curve (AUC) for each measure for each patient. We will analyze AUC summaries with univariate linear models. In our main analysis we will analyze the series of functional status measures using linear mixed models that predict the outcome from time, independent variables and their interaction. We will repeat the analyses described for path c, this time by including treatment received in the models. We will test if the observed effects of DCS, CPS or trust on outcomes will be weaker after controlling for treatment. These analyses will be performed within and between groups (intervention and usual care controls). Specific Aim 3: Hypothesis: Prostate cancer patients in the intervention group undergoing conjoint analysis-value clarification exhibit improved treatment choice, satisfaction with decision, lower regrets, and improved objective and subjective outcomes. Analysis for Specific Aim 3 uses intent-to-treat approach: all randomized participants will be included regardless of whether they drop out of the intervention or study. Analysis will involve comparison of the primary outcomes between intervention and usual care control groups. Improved treatment choice is operationalized as the likelihood of low-risk PCa patients receiving active surveillance than active treatment, and will be compared between intervention and usual care control group. To allow for different trajectories of the outcome measures and to afford flexibility in making contrasts within participants over time and across participants, while simultaneously controlling for potential confounders, we propose the participant-specific or mixed effects linear model, in which the mean outcome depends on fixed covariates and random effects. The primary fixed effects will be indicators for intervention group and hospital. We will also stratify the analysis by type of treatment. The random effects represent the unobserved factors that lead to variation of the individual participants outcome. Random intercepts for each participant permit modeling of natural variation across participants at baseline. In addition, random slopes or random effects for the trajectory of each participant over time, allow for variation of each participant about a mean, overall trajectory across all participants. Although less robust to model misspecification, the mixed effects paradigm offers special flexibility in longitudinal data when exposures vary over time and when dropout and missed visits lead to unbalanced groups. The target of inference is the participant-specific response to treatment over time. At each time point of interest, we will estimate from the fitted model the difference from baseline in outcome for the treatment and control groups and test the difference between these differences. Both univariate and multivariate results will be reported in terms of Wald test, point estimates, and 95% confidence intervals. Specific Aim 4: Hypothesis 4: Prostate cancer patients whose treatment is more concordant with their values markers will experience improved subjective and objective outcomes. This specific aim s for intervention group only. We will analyze the association of the concordance between stated individual preferences and actual treatment received with objective (PCa recurrence and complications), subjective (HRQoL, psychological wellbeing, SWD, and satisfaction with care) outcomes, across treatment groups, adjusting for covariates. Association between the value markers (profiles) and measures of outcomes and personal and clinical characteristics: The value markers will be studied for their relationship with socio-demographic and clinical characteristics. We will also assess the association of value markers with outcomes. We will perform logistic regression with outcomes as the dependent variable and dummy variables for the utility-based profiles obtained earlier as independent variables. We will perform this evaluation with and without adjusting for patient attributes in the logistic model. For each case (adjusting and not adjusting for patient attributes), the evaluation of association between these profiles and outcomes will be based on a likelihood ratio test of the set of odds ratios corresponding to the dummy variables of the profiles. Additionally, we will perform a sequence of pair wise tests of comparisons of the profiles in terms of the proportion of type of treatment received based on the Holms multiple comparisons approach. This procedure is hierarchical in that it will identify the utility-based profile at the start of the process before making other comparisons, thus protecting the Type I error from additional comparisons. Specifically, Holms approach tests each pair-wise comparison in ascending order of p-values. Successively larger p-values have less rigorous alpha. The sequential Holm tests terminate after the first non-significant comparison so no subsequent comparison is significance. Concordance and its assessment: Understanding and respect for the patients preference and values is the main aspect of concordance [69, 73]. Thus a first step in concordance involves the physician extracting and understanding the patients view, followed by an agreement between the physician and patient regarding a management plan that integrates their views. There exist many definitions of concordance. For the purpose of this study, we operationalized concordance as agreement between a patients value markers and the attributes (or characteristics) of the treatment that

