
the patient receives (choice). Association of concordance between stated preference and attributes of treatment received will be studied separately for each treatment using Kappa statistics. The degree of concordance then will be used as an independent variable to test its association with outcomes. For objective/clinical outcomes (i.e., complications and PCa recurrence), we will test the hypothesis that degree of concordance is associated with PCa recurrence (measured by PSA doubling time). To evaluate the effects of concordance on biochemical recurrence of PCa, we will analyze PSA levels on the log scale over time using a mixed model approach. We also will apply survival analyses (Kaplan-Meier, logrank and Cox model) to model effects concordance of treatment and covariates on time to PSA recurrence. For subjective outcomes of urologic symptoms (AUA-SI), generic and prostate specific HRQoL, psychological well-being (CES-D, MAX-PC), satisfaction with decision and satisfaction with care, we will perform inferential analysis with t, chi-squared and non-parametric tests. Wilcoxon matched-pairs test will be used for comparisons within concordance and non-concordance groups. A concordance group will be defined as at least 75% agreement between values markers and treatment related attributes. We will perform sensitivity analysis to test robustness of results. Primary analyses will compare baseline with six and 24 months assessments, as literature suggests these are the clinically most relevant time points. Secondary analyses will compare baseline with three month and one year outcomes. Proportion returning to baseline over time will be compared using chi-squared tests, using procedures such as Bonferroni, Scheffé, and step-down Holm corrections to adjust for multiple testing. We will use loglinear regression models with psychological well being, HRQoL and satisfaction with care scores (log) as dependent variables, logistic regression with return to baseline as the dependent variable, and degree of concordance as the independent variable. For repeated measures outcomes we will use linear mixed models (Proc Mixed).

The following documents are currently attached to this item:

There are no documents attached for this item.

Deception

Does your project use deception?

No

Data confidentiality

- x Paper-based records will be kept in a secure location and only be accessible to personnel involved in the study.**

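### For the Aim 4 link between preference profiles and outcomes, the plan names only logistic regression; this conflicts with its own linear-model rule for scores and would force an unstated cut

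*Combined protocol and SAP*

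**What the plan says.** **The profile analysis.** In the Analysis Plan, Specific Aim 4, the model is: "We will perform logistic regression with outcomes as the dependent variable and dummy variables for the utility-based profiles obtained earlier as independent variables". Inference is a likelihood ratio test of the profile odds ratios, with and without adjustment for patient attributes. No cut-point, visit or separate rule for scores is given.

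**Its power statement.** Under Accrual, power for profiles is worked out for "a binary outcome (e.g. recovery of baseline HRQoL) with a 2-sided alpha of .0125 (Holms adjustment profiles", with allocations of "25 in one vs. 10 in other profile) and less conservative allocation (35 in one profile vs. 35 in other profile". The result is that "the group difference of 0.56 yields 80% power; for the second allocation an effect size of 0.42 corresponds to power of 90", and the conclusion is that "with our anticipated effect size of 0.51, we will have adequate power with $n=60$ in each group".

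**Text that points the other way.** The general paragraph that opens the Analysis Plan assigns general linear methods, including mixed models, to uncensored continuous outcomes, and lists HRQoL, psychological wellbeing and satisfaction with care among them. The last part of Aim 4 has models for log scores, a logistic model for return to baseline, and linear mixed models for repeated measures. The first two have degree of concordance as explanatory variable. The sentence on mixed models names no explanatory variable but follows directly on them.

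**The outcomes.** Aim 4 covers both events (recurrence, complications) and scores (HRQoL, wellbeing, satisfaction with decision and with care).

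**The concern.** Logistic regression on profile dummies needs a categorical outcome. For events that is natural. For a scale score it means choosing a threshold and a visit, and the plan states neither. Those choices could then be made after the data are seen, and information collected at the other visits would go unused.

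The cost falls where the plan is thinnest. The power statement works with profiles of 10 to 35 men, while the same section calls standardised differences of 0.5 to 0.87 clinically relevant. If the binary test can detect only much larger shifts at those sizes, a relevant association between profile and quality of life would probably be missed, although the same men's scores could show it.

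**Working it through.** **Inputs from the Accrual section:** two-sided alpha 0.0125 for profiles (z = 2.498); allocations 25 vs 10 and 35 vs 35; "We assume a conservative intra-class correlation of 0.3 and 4 follow-up measures per subject"; SD 8 to 14; 10% dropout; relevant standardised differences (SMD) 0.5 to 0.87. The intervention arm has 360 men, and Aim 4 uses that arm only.

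**Assumptions of this check:** normal scores with equal SD, compound symmetry, a profile effect constant over visits, a two-profile contrast, and no dropout in steps 3 to 5.

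**1. The plan's profile power.** Read as differences in proportions, with a pooled normal test and an assumed base rate of 0.15 (none is given):
- 25 vs 10, 0.15 vs 0.71: 78.7% (stated 80%).
- 35 vs 35, 0.15 vs 0.57: 90.2% (stated 90%).

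Over all base rates the ranges are 74-91% and 87-98%. Read as SMDs, the same effects would give 16% and 23%, so they must be differences in proportions.

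**2. The plan's HRQoL power, to confirm the repeated-measures model.** Variance factor for the mean of four visits: (1 + 3 × 0.3)/4 = 0.475. Detectable difference = (1.96 + 0.84) × 8 × √(2 × 0.475/n). With 10% dropout, n = 324 gives 1.21 points and n = 54 gives 2.97, matching the stated 1.2 and 3.0 (at SD 8).

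**3. What the profile differences mean on the score scale.** With rates centred on 0.5:
- 0.56 is z(0.78) − z(0.22) = 1.54 SD.
- 0.42 is z(0.71) − z(0.29) = 1.11 SD.

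The t-test at the same allocation and power needs the following (four-visit mean = one visit × √0.475):

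| Allocation, power | Binary | One visit | Mean of four |
|---|---|---|---|
| 25 vs 10, 80% | 1.54 SD | 1.31 SD | 0.90 SD |
| 35 vs 35, 90% | 1.11 SD | 0.92 SD | 0.64 SD |

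Information kept at 25 vs 10: (1.31/1.54)² = 72% of one visit, and (0.90/1.54)² = 34% of the four-visit mean.

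**4. General result for a cut.** Information kept = φ(c)²/[p(1−p)]. A median cut keeps 64% of one visit. Against the four-visit mean, multiply by (1 + 3 × ICC)/4: 30% at ICC 0.3, 40% at 0.5, 49% at 0.7. At ICC 0.3, using one visit instead of four loses 52.5% with no cut at all.

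**5. Power at the plan's relevant differences, alpha 0.0125, ICC 0.3.** Example, SMD 0.5, 35 vs 35:
- Median cut: rates 0.401 vs 0.599; (0.197 − 2.498 × 0.1195)/0.1172 = −0.86, so 19%.
- One visit: 0.5 × √(35/2) − 2.498 = −0.41, so 34%.
- Four-visit mean: 2.092/√0.475 − 2.498 = 0.54, so 70%.

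| SMD, allocation | Median cut, one visit | Continuous, one visit | Mean of four |
|---|---|---|---|
| 0.5, 35 vs 35 | 19% | 34% | 70% |
| 0.5, 25 vs 10 | 7% | 12% | 29% |
| 0.5, 180 vs 180 | 90% | 99% | about 100% |
| 0.87, 35 vs 35 | 63% | 87% | 99.7% |
| 0.87, 25 vs 10 | 24% | 43% | 81% |

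**6. Return to baseline itself, by simulation.** Assumed: 324 men in two equal profiles, 3-point difference, SD 8, mean drop 5 points, alpha 0.05. Over repeated runs, return to baseline at 24 months had 58-60% power at ICC 0.3 and 80-83% at ICC 0.6. An unadjusted change score had 83% and 97%; the baseline-adjusted score had 94% and 98-99%. Part of the gain is therefore baseline adjustment, not removal of the cut.

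**The case against.** The plan can be defended on several counts.

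- **The general rule may govern.** The opening of the Analysis Plan gives linear and mixed models for continuous outcomes throughout, and Aim 4 ends with linear mixed models for repeated measures. This stands in part: the plan is inconsistent for profiles rather than plainly committed to dichotomising. But the profile paragraph is the specific text, its test is on odds ratios, and its power line is binary, so the general rule does not clearly override it.
- **Return to baseline is not the named profile model.** A reader might infer that it is, because Aim 4 contains "logistic regression with return to baseline as the dependent variable". That sentence has degree of concordance as its explanatory variable; for profiles, recovery of baseline HRQoL is only the example in the power statement. This stands.
- **The loss can be overstated.** A reader might infer that most of the trial's power is thrown away. The documents do not support that. With 180 vs 180 men the loss is small, and much of the two-thirds comes from using one visit.
- **Four visits may be the wrong comparator.** The concordance text makes six and 24 months primary. With those two visits at ICC 0.3 the factor is (1 + 0.3)/2 = 0.65, and a one-visit median cut keeps 0.64 × 0.65 = about 41%. The loss is smaller but still more than half.
- **Events are not scores, and return to baseline is easy for patients to interpret.** Both are right. Logistic regression suits complications, and return to baseline is worth reporting.
- **Hypothesis 4 concerns concordance;** the profile analysis is an additional assessment. This limits the importance of the point but does not remove it, since the plan gives that analysis its own power calculation.

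**Conclusion.** The point holds as a conflict within the plan that has a real cost in efficiency. For profiles and score outcomes, the specific text names only logistic regression while the general text assigns linear and mixed models, and the threshold and visit needed to follow the specific text are missing.

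If the specific text is followed, dichotomising costs about 28-36% of the information in one visit. The total is about two-thirds against the four-visit mean at ICC 0.3, and about half at ICC 0.7. The consequence for power depends on profile size: large at the plan's 25 vs 10 and 35 vs 35, small for an even split of the whole arm. These figures rest on the assumptions listed with the calculation. The base rates and the 0.6 and 0.7 correlations are not in the documents.

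**What to change.** In Specific Aim 4, split the profile analysis by outcome type.

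- **Scores:** use the linear mixed model already planned, with profile, visit, profile-by-visit and, where one exists, the baseline score. Test the profile terms jointly.
- **Complications:** keep logistic regression on the profile dummies.
- **Time to recurrence:** use the survival methods already planned.
- **Return to baseline:** keep as a supportive analysis, with its threshold and visit fixed in advance.

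Under Accrual, restate the profile power for scores in points or SD units, with the assumed profile sizes. The present allocations total 35 or 70 men, while the conclusion refers to 60 per group; these should be reconciled in the same edit.

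The cost is wording, a new power line and a little more analysis work; no new data are needed. The drawback is that return to baseline, which is easily understood, becomes supportive.

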Characteristics of the Study Population

Target population

Study Population: We will use stratified randomized control trial to study association between value markers and objective (complications and cancer recurrence) and subjective (HRQoL, psychological wellbeing) outcomes across intervention groups, over 24 month period. We will recruit newly diagnosed localized PCa patients from UPHS (Hospital of University of Pennsylvania, Presbyterian Medical Center, and Pennsylvania Hospital), Fox Chase Cancer Center and Philadelphia Veterans Administration Medical Center (PVAMC) and randomize them to conjoint analysis intervention (n=360) or control group (n=360). Participants: The sample will consist of 720 newly-diagnosed PCa patients.

Subjects enrolled by Penn Researchers

580

Subjects enrolled by Collaborating Researchers

220

Accrual

Participant availability: UPHS is a large hospital and physician network in greater Philadelphia area. Approximately 1,600 patients with newly diagnosed PCa are evaluated annually: 40-50% undergo surgery (RP or RALP); 30-40% undergo EBRT or BT; 10-20% undergo PT. The urology clinic at the Hospital of the University of Pennsylvania (HUP) treats more than 60% of this group; the rest are treated at Presbyterian Medical Center and Pennsylvania Hospital. Additionally, UPHS has a proton therapy center, providing a unique opportunity to study this new technology. The Philadelphia Veterans Administration Medical Center (PVAMC) cares for 33,000 veterans in Philadelphia area and evaluates ~400 patients with newly diagnosed PCa each year. Fox Chase Cancer Center evaluates ~500 patients with newly diagnosed PCa each year. Together, UPHS, PVAMC, and Fox Chase Cancer Center provide care to socio-demographically diverse population of ~2,500 men newly diagnosed with PCa each year. Thus, our study sample requirement of 720 patients (33% of the available pool) can be fulfilled comfortably, as demonstrated by the successful recruitment for our earlier studies. We estimated sample

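### Aim 4 tests values–treatment concordance without the values profile in any model, so an outcome difference between profiles can pass for a benefit of matching

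*Combined protocol and SAP*

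**What the plan says.** Aim 4 is limited to one arm ("This specific aim s for intervention group only"). In the Analysis Plan, under the assessment of concordance, "we operationalized concordance as agreement between a patients value markers and the attributes (or characteristics) of the treatment that" the patient receives. The values markers are the latent profiles derived in Aim 1. The plan then states: "The degree of concordance then will be used as an independent variable to test its association with outcomes".

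The analyses listed are:
- t, chi-squared and non-parametric tests for the subjective outcomes
- loglinear models of scores
- logistic models of return to baseline
- mixed models
- Kaplan-Meier, log-rank and Cox analyses of PSA recurrence.

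The loglinear and logistic models name degree of concordance as the independent variable. Adjustment is promised only for unspecified covariates. Section D.2.4.4 lists disease severity, Gleason score, comorbidity and demographics as potential confounders; the values profile is not among them.

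Profiles are related to outcome elsewhere in Aim 4: "We will also assess the association of value markers with outcomes". That is a logistic model with profile indicators and no concordance term. The power text under Accrual covers this profile comparison and concludes that "with our anticipated effect size of 0.51, we will have adequate power" with 60 per group.

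**The concern.** A matching effect is an interaction: something gained from the pairing of a profile with a treatment, beyond what each contributes alone. A test that leaves out the profile asks only whether men with high and low concordance have equal outcomes. That can be false with no matching effect at all. It is enough that one kind of patient tends to recover better whatever he receives, and that his kind is matched more often.

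A significant coefficient would be read as evidence that aligning treatment with values helps, which is half of the study hypothesis in the Abstract. It might show only which men value what. The bias can also run the other way: if the profile matched more often does worse, a real benefit could be hidden.

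**Working it through.** **The plan's own figures.** The Accrual section gives 80% power for a difference of 0.56 (25 vs 10 men) and 90% for 0.42 (35 vs 35), at two-sided alpha 0.0125 (z = 2.498). I read these as differences in proportions. The base rate is not given; I assume 0.40. Power = Φ[(d − z·s0)/s1], with s0 the pooled and s1 the unpooled standard error.
- 25 vs 10: pooled proportion (25×0.40 + 10×0.96)/35 = 0.56; s0 = 0.1857; s1 = 0.1159; (0.56 − 0.4639)/0.1159 = 0.83, so 79.6%.
- 35 vs 35: pooled proportion 0.61; s0 = 0.1166; s1 = 0.1052; (0.42 − 0.2912)/0.1052 = 1.22, so 88.9%.

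Read as standardised mean differences, the same inputs give 15.8% and 22.9%. The proportion scale fits better, but the text does not settle it, so both are shown below.

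**Inputs for the concordance test.**
- From the documents: 360 men in the intervention arm; "Within treatment type, the sample size is reduced to 60 per intervention arm"; "The sample size is adjusted to accommodate a 10% missing or dropout rate by 24 months", so I use 324 men, 54 per treatment; intra-class correlation 0.3; four follow-up measures; alpha 0.05.
- Assumed: three equal-sized profiles favouring surveillance (one option), surgery (two) or radiation (three); treatment received independent of profile; no matching effect; profile means of −d/2, 0 and +d/2, rising with match rate. I take d = 0.51, and about half of it, 0.25.

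**Bias.** With equal quotas the match rates are 1/6, 2/6 and 3/6, with mean 1/3. Var(C) = 1/3 × 2/3 = 2/9, so n·Var(C) = 324 × 2/9 = 72.
- Cov(C, profile mean) = (1/3) × 2 × (1/6) × (d/2) = d/18.
- Expected concordance coefficient with no matching effect: b = (d/18)/(2/9) = d/4, which is 0.1275 for d = 0.51 and 0.0625 for d = 0.25.

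**Rejection rate.** SE = √(residual variance/72); rejection = Φ(b/SE − 1.96) + Φ(−b/SE − 1.96). Residual variance is the total outcome variance less b² × 2/9. The total is 1 + d²/6 for one visit, 0.475 + d²/6 for a four-visit mean (0.3 + 0.7/4 = 0.475), and 0.25 for a binary outcome centred on 50%.

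| d | Outcome | Residual variance | SE | b/SE | Rejection |
|---|---|---|---|---|---|
| 0.51 | standardised, one visit | 1.040 | 0.120 | 1.06 | 19% |
| 0.51 | standardised, four-visit mean | 0.515 | 0.085 | 1.51 | 33% |
| 0.51 | difference in proportions | 0.246 | 0.059 | 2.18 | 59% |
| 0.25 | standardised, one visit | 1.010 | 0.118 | 0.53 | 8% |
| 0.25 | standardised, four-visit mean | 0.485 | 0.082 | 0.76 | 12% |
| 0.25 | difference in proportions | 0.249 | 0.059 | 1.06 | 19% |

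Simulations with equal quotas and three profiles gave 17–66% for 0.51 and 8–21% for 0.25. Treatment terms alone do not help, because in this layout every treatment has the same match rate of 1/3. With profile terms added, rejection was 4–6%.

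**Where there is no inflation.** With two equal-sized profiles and equal concordance rates, rejection was about 5%. With four profiles whose match rates do not line up with outcome (0.7, 0.5, 0.5, 0.7) it was also about 5%; with rates rising from 0.5 to 0.7 alongside outcome it was 23%. If the model has treatment terms, concordance must be unrelated to profile within treatment: equal overall rates with a 70:30 profile split still gave 13% for a 0.51 difference in proportions.

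**Within one treatment.** If concordance is set by profile, then among men on a single treatment it is the same variable as profile membership. With 60 men, a pure profile effect of 0.51 is declared a concordance effect 93–99% of the time as a difference in proportions, or 35–51% as a standardised difference (profile splits from 50:50 to 80:20). Adding a profile term cannot separate the two there.

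**The case against.** Several counter-arguments have force.

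- **Clinic mix.** A reader might infer unequal match rates from the uneven treatment mix quoted for UPHS (surgery 40–50%, proton therapy 10–20%). The documents do not support this. Those figures describe patients evaluated in the clinics, whereas the recruitment text fills 60 per treatment in each arm. Unequal match rates remain possible under equal quotas, as the layout above shows, but they are an assumption.
- **Meaning of 0.51.** A reader might take it as a profile effect that holds whatever the treatment. The text ties it to groups of 60, which is the size within one treatment and arm, where a profile contrast and a concordance contrast can coincide. So 0.51 may already contain matching. It shows that the plan thought profile differences likely enough to power, but not that they are free of treatment. As a difference in proportions (24.5% vs 75.5%) it would be a very large main effect. The plan also says adjustment for patient characteristics may shrink it.
- **Change from baseline.** The primary comparisons set baseline against 6 and 24 months. A stable difference in score level between profiles cancels in change. The models of scores stay exposed, and so does any analysis where profiles differ in recovery.
- **Open covariate wording.** Adjustment for covariates is promised without a closed list, and sensitivity analysis is planned. A profile term is therefore not excluded, but none is named, and the t, chi-squared and rank tests cannot carry one.
- **Association only.** Aim 4 is non-randomised and its methods speak of association. That makes this confounding of the intended reading. Hypothesis 4 is nevertheless worded as improvement from concordance.

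**Conclusion.** The structural point stands. As written, Aim 4 cannot separate a matching effect from a profile main effect, because concordance is built from the profile and no concordance analysis contains it.

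The size is conditional. Under equal quotas and three assumed profiles whose outcomes rise with match rate, a nominal 5% test rejects about 8–20% of the time for a profile spread of 0.25 and about 17–65% for 0.51, with no matching effect. There is no inflation if concordance is unrelated to profile. The number of profiles, their match rates, their ordering and the scale of 0.51 are all assumptions.

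A reader might go further and infer that the plan predicts a false-positive result, or that Type I error is shown to be uncontrolled. The documents do not support that: they give no concordance rates by profile and do not say that 0.51 is independent of treatment. The change should be made because it is cheap and the present test does not answer Hypothesis 4.

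**What to change.** Define the test of Hypothesis 4 as the concordance coefficient in regression, mixed or Cox models pooled across treatments, with both treatment-received indicators and the Aim 1 values-profile indicators included. Label as descriptive the unadjusted t, chi-squared, non-parametric, Kaplan-Meier and log-rank comparisons. Do the same for any concordance analysis within a single treatment, where profile-level concordance cannot be told apart from profile.

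The cost is SAP wording and a few indicators that Aim 1 already produces. The confidence interval for concordance will generally widen, because profile takes up part of its variation. In the layout above, the variance of concordance left after profile and treatment is 2/9 − 1/54 = 11/54, so n × variance falls from 72 to 66. The one-visit SE goes from 0.120 to √(1/66) = 0.123. The loss will be larger if profile and treatment together determine concordance more closely.
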